### 11.1 Exposure

Tables with descriptive statistics in accordance with section 7.1 will be presented for the following parameters:

- actual duration ABBVIE REGIMEN (in days);
- the number of patients with collected deviating duration reasons;
- adherence ABBVIE REGIMEN (calculated for Paritaprevir/R-Ombitasvir, Dasabuvir and Ribavirin separately):
  - percentage of target dose taken in treatment intervals (weeks 1-4, 5-8 and 9-12) for Paritaprevir/R-Ombitasvir and for Dasabuvir;
  - percentage of patients who missed of study drug administration for at least 7 days in a row (only for Paritaprevir/R-Ombitasvir and Dasabuvir).

All corresponding listings will be presented.

### 11.2 Adverse Events

Only treatment-emergent adverse events will be analyzed.

*Treatment-emergent AE* is any reported event that begins or worsens in severity after initiation of study drug through 30 days post-study drug dosing.

All analyzed AEs will be coded using the MedDRA version 20.0 (or further updating) and tabulated in the report with grouping by primary system organ class (SOC) and preferred term (PT).

The frequency of a specific AE occurrence will be presented by the proportion of patients with this AE emergence as well as the total number of episodes this AE for a diagnosis.

The following tables with descriptive statistics in accordance with section 7.1 will be presented:

- all AE / SAE;
- AE / SAE by severity;
- AE / SAE by relationship to the study drug.

Tables of AE/SAE by severity (relationship to the study drug) will be prepared using the following rules. Each SOC / PT category will include only the AEs with the highest severity (relationship to the drug) in each patient, while in the Total category all AEs of this patient will be considered. At the same time, each patient will be counted only once with highest severity (relationship to the study drug) in each SOC and each PT level as well as Total level.

Also all AEs will be presented in listings. Additional listings for unintended medication errors will be provided.

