9.7.7 Tolerability Analysis

All tolerability variables will be summarized using descriptive statistical methods for the SP stratified by type of combination treatment and scheduled treatment duration.

All SAEs, non-serious AEs and pregnancy occurrences are to be reported for patients included in the study (see Section 11.0 and 9.2.3). AEs will be coded using MedDRA. The number and percentage of patients with treatment-emergent AEs (i.e. any reported event that begins or worsens in severity after initiation of study drug through 30 days post-study drug dosing) will be tabulated by primary MedDRA SOC and PT. Corresponding summary tables will be provided for all serious treatment-emergent AEs. The tabulation of the number of patients with treatment-emergent AEs by severity and relationship to study drug will also be provided. Patients reporting more than one AE for a given MedDRA PT will be counted only once for that term using the most severe incident for the severity summary table and the most related for the relationship summary table. Patients reporting more than one type of event within a SOC will be counted only once for that SOC.

Additional details of the analysis of AEs will be specified in the SAP.

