The inclusion period will be approximately 8 months and the observational period of the study will be from baseline visit until 24 weeks post-treatment. The observational period for patients receiving 12 weeks of ABBVIE REGIMEN will be maximum 36 weeks (12 weeks treatment and 24 weeks post-treatment observation) and for patients receiving 24 weeks of ABBVIE REGIMEN the observational period will be maximum 48 weeks (24 weeks treatment and 24 weeks post-treatment observation).

Both regimens include four visits and several time windows for interim data collection (two for 12-week and three for 24-week). Data documented will be those closest to these time windows.

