## 11 Safety analysis

Safety analysis will be conducted on *the safety population (SP)*. The results will be reported overall and for scheduled treatment combination ( $\pm$  RBV) and duration (12 or 24 weeks) groups.

The following parameters will be analyzed:

- study drug exposure;
- adverse events;
- pregnancies;
- clinical laboratory evaluations.

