**Table 4.2.1 Adverse events**  
The safety population  
Page X of X

| System organ class (SOC)
Preferred term (PT) | ABBVIE REGIMEN + RBV           |              | ABBVIE REGIMEN - RBV           |              | Overall
(N=XX)
n (%) /E |
|---|--------------------------------|--------------|--------------------------------|--------------|-------------------------------|
|   | 12 weeks
(N=XX)
n (%) /E | XX(XX.X) /XX | 12 weeks
(N=XX)
n (%) /E | XX(XX.X) /XX |                               |
| Total [1]                                       | XX(XX.X) /XX                   | XX(XX.X) /XX | XX(XX.X) /XX                   | XX(XX.X) /XX | XX(XX.X) /XX                  |
| System organ class 1                            | XX(XX.X) /XX                   | XX(XX.X) /XX | XX(XX.X) /XX                   | XX(XX.X) /XX | XX(XX.X) /XX                  |
| Preferred term A                                | XX(XX.X) /XX                   | XX(XX.X) /XX | XX(XX.X) /XX                   | XX(XX.X) /XX | XX(XX.X) /XX                  |
| Preferred term B                                | ...                            | ...          | ...                            | ...          | ...                           |
| ...   | ...                            | ...          | ...                            | ...          | ...                           |
| System organ class 2                            | ...                            | ...          | ...                            | ...          | ...                           |
| ...   | ...                            | ...          | ...                            | ...          | ...                           |
| ...   | ...                            | ...          | ...                            | ...          | ...                           |

N: the number of patients in the safety population.  
n: the number of patients who have AE with appropriate SOC/PT. Percentages are calculated as (100 x n/N) .  
E: the number of AE episodes, which have an appropriate SOC and/or PT.  
Patients with several AEs having the same SOC and PT are accounted only once for appropriate SOC and PT.  
[1] The Total line displays the number (n) and the proportion (%) of patients who have at least on AE as well as the total number of AE episodes in the study.  
The coding is carried out by the dictionary MedDRA v.20.1.  
The table does not include AEs that occurred prior to the first intake of the study drug.  

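### Adverse events are tabulated by scheduled duration as crude percentages and episode counts; if a 24-week group exists, its columns cover a longer window than the 12-week columns, and no shared-window summary is planned.

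*SAP*

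**What the plan says.** SAP 11 reports safety results for the safety population overall, by use of ribavirin "and duration (12 or 24 weeks) groups". Protocol 9.7.7 likewise has tolerability "stratified by type of combination treatment and scheduled treatment duration".

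The measures are set in SAP 11.2: the frequency of an event is "presented by the proportion of patients with this AE emergence as well as the total number of episodes this AE". The footnote to the shell of Table 4.2.1 defines n as "the number of patients who have AE with appropriate SOC/PT. Percentages are calculated as (100 x n/N"), where N is the number of patients in the safety population. Tables 4.3.1 and 4.4.1 use the same formula.

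SAP 11.2 and Protocol 9.7.7 count an event as treatment-emergent if it is "any reported event that begins or worsens in severity after initiation of study drug through 30 days post-study drug dosing". SAP 4.1 gives the scheduled courses: observation lasts "maximum 36 weeks (12 weeks treatment and 24 weeks post-treatment observation") for the short course and "maximum 48 weeks (24 weeks treatment and 24 weeks post-treatment observation") for the long one.

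SAP 11.1 and Table 4.1 summarise actual treatment duration in days, but the adverse event tables do not use it. SAP 13 plans no further analyses.

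**The concern.** Describing tolerability is a secondary objective, and both documents choose to break it down by scheduled duration. Once 12- and 24-week columns exist, readers will compare them. A cumulative percentage grows with the time over which events are counted, and an episode count has no time denominator at all. A higher figure for the longer course could then reflect a higher event risk, a longer window, or both, and nothing in the planned tables separates the two. The pooled Overall column would also depend on the mix of durations.

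**Working it through.** The plan states no window length and no expected adverse event rate, so there is no figure of its own to reproduce. The check uses these inputs:

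- Scheduled treatment of 12 weeks = 84 days or 24 weeks = 168 days (SAP 4.1).
- Treatment-emergent period ending 30 days after dosing (SAP 11.2, Protocol 9.7.7).
- Assumption: a 12-week cumulative percentage p12. The documents give none, so a range is shown.

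**Windows.** 84 + 30 = 114 days; 168 + 30 = 198 days; 198/114 = 1.74. Footnote c of Protocol Table 2 ends tolerability documentation at post-treatment week 4. That gives 84 + 28 = 112 and 168 + 28 = 196 days, ratio 1.75, so the choice of limit hardly matters. All of these are scheduled lengths; early discontinuation shortens them.

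**Equal constant hazard.** p24 = 1 − (1 − p12)^(198/114). For p12 = 5%, 10%, 20% and 40%, p24 = 8.5%, 16.7%, 32.1% and 58.8%. Expected episodes per patient scale by 1.74.

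**Front-loaded hazard.** Let the hazard after day 28 be f times the hazard in days 1-28, the same in both groups. With H = −ln(1 − p12), the early daily hazard is h = H/(28 + 86f), and p24 = 1 − exp[−h(28 + 170f)]. For p12 = 20%, H = 0.223:

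| f | 24-week percentage |
|---|---|
| 1 (constant) | 32.1% |
| 0.5 | 29.9% |
| 0.25 | 27.2% |
| 0.1 | 24.0% |
| 0 (all events by day 28) | 20.0% |

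At equal hazard the longer window cannot lower the expected figure, and it leaves it unchanged only if no events occur after day 114. The 32.1% is not a ceiling: if events occurred only on treatment, at a constant rate, the figure would be 1 − 0.8^(168/84) = 36.0%.

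**Would a rate per patient-year settle it?** Under a constant hazard, yes: at p12 = 20% both groups give 71.5 first events per 100 patient-years. With early events, no. Suppose 20% of each group have their event evenly over days 1-28 (mean day 14) and none later:

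- 12 weeks: 0.2 × 14 + 0.8 × 114 = 94.0 days at risk per patient; 0.2/94.0 × 36,525 = about 78 per 100 patient-years.
- 24 weeks: 0.2 × 14 + 0.8 × 198 = 161.2 days; 0.2/161.2 × 36,525 = about 45 per 100 patient-years.

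The early risk is identical, yet the longer regimen appears to have the lower rate.

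**The case against.** **There may be no 24-week group.** The shells of Tables 4.2.1, 4.3.1 and 4.4.1, and the disposition table for everyone who consented, name only two 12-week columns and Overall. Adherence in SAP 11.1 stops at week 12. The SAP is dated February 2018, after the planned end of data collection in August 2017, and SAP 16 already relies on what the data show about use of the support programme. The 12-week columns may therefore describe the actual cohort. This stands as a condition on the point. It does not remove it, because the SAP still provides for 24-week patients in its end-of-treatment window (5.2), its population cut-offs (6) and its safety strata (11), and it leaves further treatment-group tables open.

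**Nothing is compared.** Tolerability is only described, no test or contrast between durations is planned, and a crude percentage is a valid description of risk over a full course. This also stands, and it is why the crude percentages should stay. It does not help a reader who looks across the columns.

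**Exposure is already shown.** Table 4.1 gives actual duration for the same groups, so the difference in exposure is visible. A reader still cannot turn percentages by organ class or preferred term into figures over equal time.

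**The hazard is unlikely to be constant.** Protocol 7.1 describes bilirubin elevations that peak by week 1. This stands, and it is why a range is shown.

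**Early stoppers.** Their shortened windows enter the same denominator, but the documents allow no estimate of the effect, and those who stop because of an event are already in the numerator.

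**Conclusion.** The point holds as a conditional and inexpensive improvement. If the safety population includes 24-week patients, the planned columns cover scheduled windows of about 114 and 198 days, and at equal hazard the 24-week percentages and episode counts are expected to be as high or higher. For a 12-week figure of 20%, the 24-week figure is 20.0% when all events fall in the first 28 days and 32.1% under a constant hazard. This rests on equal hazards in the two groups and on completed courses; neither document gives adverse event rates or the number of 24-week patients.

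A reader might infer that the longer regimen must look worse by a fixed amount, such as 74% more episodes. The documents do not support that: 1.74 is the ratio of the windows and becomes the ratio of episodes only under a constant event rate. Nor do they support saying that every adverse event table sets 12 and 24 weeks side by side, since the printed shells show no 24-week column. A reader might also infer that patient-year rates cure the problem, but for early events they favour the longer regimen. The primary endpoint is not affected.

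**What to change.** - Keep the crude percentages and label them as risk over the full course.
- Count the 24-week patients in the safety population. If there are none, no shared-window table is needed.
- If there are any, add one table giving, for the Total, organ class and serious event lines, the percentage of patients with an event, and the episodes, in a window both groups share, such as days 1-84 of treatment. This needs no assumption about the hazard.
- Footnote the unequal full windows in the 4.2, 4.3 and 4.4 series of tables.
- Show rates per 100 patient-years only as a supplement, with a note that they assume a roughly constant hazard and would favour the longer regimen if events come early.
- State that differences between durations are described and not attributed to duration. Duration follows patient characteristics (Protocol 9.7.2 links it to subtype, fibrosis status and treatment history), so neither measure removes confounding.

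The cost is SAP wording and one extra table from treatment and event dates already collected. Incomplete event start dates will need a rule for placing them inside or outside the shared window, because SAP 7.3 only classifies them as before or during the study period.

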### **11.3 Pregnancies**

Female subjects will be tested for pregnancy at each study visit. The results of these tests and pregnancies episodes will be reported in the listing.

### **11.4 Clinical Laboratory Evaluations**

Clinical laboratory evaluations include the following parameters:

- hematology results;
- blood chemistry results.

The following parameters, which are evaluated at each study visit, will be analyzed in tables and presented in listings:

- hematology:
  - hemoglobin;
  - platelets;
  - prothrombin time (seconds);
  - prothrombin time (INR);
- blood chemistry:
  - ALT;
  - AST;
  - GGT;
  - total bilirubin;
  - alpha-1-fetoprotein;
  - albumin;
  - creatinine;
  - creatinine clearance.

The results of clinical laboratory evaluations statistical analysis will be represented in accordance with section 7.1 as the following outputs:

- tables with descriptive statistics of measurement values and changes from baseline visit;
- frequency tables of out of range and clinically significant evaluates will be presented;
- shift tables based on clinical evaluation of measurements at baseline visit.

### **11.5 Other Safety Measures**

No other safety measures will be analyzed in this study.

### **12 Pharmacokinetics**

No pharmacokinetic and pharmacodynamic parameters will be analyzed in this study.

### **13 Other analyses**

No other analyses will be performed in this study.

### **14 Interim analyses and data monitoring**

No interim analysis is planned for this study.

### **15 Technical details and reporting conventions**

Statistical analysis will be performed using SAS 9.4.

One (final) statistical analysis report will be prepared in the Microsoft Office Word (.docx) format after the end of data collection and database lock. The results of statistical analysis will be presented in the form of tables, figures and listings in English.

### **16 Summary of changes to the Protocol**

The analyses methods in this SAP is fully consistent with the clinical study Protocol. The MLR analysis for the PSP results will not be performed due to lack of main predictor variability (the fact of the PSP usage is always “Yes”).

**P15-743 (HCV RWE) \_ STATISTICAL ANALYSIS PLAN \_ final 2.0 \_ 02 Feb 2018**

**18 Tables shells**

**Subject disposition**

AbbVie LLC  
P15-743 (HCV RWE)  
**Table 1.1 Subject Disposition**  
All patients  
Page X of X

|  | ABBVIE REGIMEN + RBV
12 weeks
n (%) | ABBVIE REGIMEN - RBV
12 weeks
n (%) | Overall
n (%) |
|--|---|---|------------------|
| Subjects who signed the Consent for use/disclosure of data form (informed consent) | XX  | XX  | XX               |
| The target population (TP)   | XX (XX.X)                                 | XX (XX.X)                                 | XX (XX.X)        |
| The core population (CP)   | XX (XX.X)                                 | XX (XX.X)                                 | XX (XX.X)        |
| The safety population (SP)   | XX (XX.X)                                 | XX (XX.X)                                 | XX (XX.X)        |
| The non-core population (NCP)  | XX (XX.X)                                 | XX (XX.X)                                 | XX (XX.X)        |
| The core population with sufficient follow-up data (CPSFU)                         | XX (XX.X)                                 | XX (XX.X)                                 | XX (XX.X)        |

n: the number of subjects within a specific category.  
Percentages were calculated from the number of subjects who signed the Consent for use/disclosure of data form (informed consent) overall and in the treatment groups.

Program code, date, time

Data extracted: DD.MM.YYYY

**P15-743 (HCV RWE) \_ STATISTICAL ANALYSIS PLAN \_ final 2.0 \_ 02 Feb 2018**

Abbvie LLC  
P15-743 (HCV RWE)  
**Table 1.2 The reasons of early withdrawal**  
The target population  
Page X of X

|  | ABBVIE REGIMEN + RBV
12 weeks
(N = XX)
n (%) | ABBVIE REGIMEN - RBV
12 weeks
(N = XX)
n (%) | Overall
(N = XX)
n (%) |
|--|---|---|------------------------------|
| Subjects with HCV RNA assessment performed at least 10 weeks post-treatment (i.e. >= 70 days after EoT)    | XX (XX.X)   | XX (XX.X)   | XX (XX.X)                    |
| Subjects without HCV RNA assessment performed at least 10 weeks post-treatment (i.e. >= 70 days after EoT) | XX (XX.X)   | XX (XX.X)   | XX (XX.X)                    |
| Reason if HCV RNA assessment on SVR12 not done:  |   |   |                              |
| Failure to return  | XX (XX.X)   | XX (XX.X)   | XX (XX.X)                    |
| Insufficient virological response  | XX (XX.X)   | XX (XX.X)   | XX (XX.X)                    |
| Withdrawn consent  | XX (XX.X)   | XX (XX.X)   | XX (XX.X)                    |
| Death  | XX (XX.X)   | XX (XX.X)   | XX (XX.X)                    |
| ....   | ....  | ....  | ....                         |

N: the number of subjects in the target population.

n: the number of subjects within a specific category. Percentages were calculated as (100 x n/N).

Program code, date, time

Data extracted: DD.MM.YYYY

**P15-743 (HCV RWE) \_ STATISTICAL ANALYSIS PLAN \_ final 2.0 \_ 02 Feb 2018**

Abbvie LLC  
P15-743 (HCV RWE)  
**Table 1.3 Violation of eligibility criteria**  
The target population  
Page X of X

|  | ABBVIE REGIMEN + RBV          |  | ABBVIE REGIMEN - RBV          |     | Overall
(N = XX)
n (%) |
|--|-------------------------------|--|-------------------------------|-----|------------------------------|
|  | 12 weeks
(N = XX)
n (%) |  | 12 weeks
(N = XX)
n (%) |     |                              |
| Patients with violation of inclusion criteria  | XX (XX.X)                     |  | XX (XX.X)                     |     | XX (XX.X)                    |
| Inclusion criterion #1   | XX (XX.X)                     |  | XX (XX.X)                     |     | XX (XX.X)                    |
| Inclusion criterion #2   | XX (XX.X)                     |  | XX (XX.X)                     |     | XX (XX.X)                    |
| ...  | ...                           |  | ...                           |     | ...                          |
| Patients with violation of exclusion criteria  | XX (XX.X)                     |  | XX (XX.X)                     |     | XX (XX.X)                    |
| Exclusion criterion #1   | XX (XX.X)                     |  | XX (XX.X)                     |     | XX (XX.X)                    |
| Exclusion criterion #2   | XX (XX.X)                     |  | XX (XX.X)                     |     | XX (XX.X)                    |
| ...  | ...                           |  | ...                           |     | ...                          |
| Subject has fulfilled all the inclusion and does not meet any exclusion criteria and is eligible for the trial | XX (XX.X)                     |  | XX (XX.X)                     |     | XX (XX.X)                    |
|  |                               |  |                               | ... |                              |

N: the number of subjects in the target population.  
n: the number of subjects within a specific category. Percentages are calculated as (100 x n/N).

Program code, date, time

Data extracted: DD.MM.YYYY

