AEs will be coded using the Medical Dictionary for Regulatory Activities (MedDRA) and will be tabulated by primary MedDRA system organ class (SOC) and preferred term (PT). For treatments, surgical and medical procedures the international non-proprietary name (INN) Drug Terms and Procedures Dictionary will be used.

9.7

Data Analysis

9.7.1

Analysis Population, Time Windows and Handling of Missing Data

The target population (TP) is defined as all patients who fulfill the criteria specified in Section 9.2.1. The core population (CP) is defined as all patients of the TP, who have started the treatment combination recommended in the current local label for their disease characteristics. Patients not receiving the treatment recommended in the local

Confidential Information

No use or disclose outside AbbVie is permitted without prior written authorization from AbbVie

Version 3.0 (22 Apr 2015) – country v 1.0 dated 26.06.2015

Page 32 of 61

label will be summarized in the non-core population (NCP). In addition, the core population with sufficient follow-up data (CPSFU) is defined as all CP patients, who fulfil one of the following criteria:

- (1) evaluable HCV RNA data ≥ 70 days after the last actual dose of the ABBVIE REGIMEN (i.e. data within the SVR12 time window)
- (2) a HCV RNA value ≥ 50 IU/mL at the last measurement post-baseline (i.e. no virological response achieved at the last measurement on-treatment or post-treatment)
- (3) HCV RNA < 50 IU/mL at the last measurement post-baseline, but no HCV RNA measurement ≥ 70 days after the last actual dose of the ABBVIE REGIMEN due to reasons related to safety (e.g. dropped out due to AE) or incomplete efficacy information (e.g. virologic failure such as relapse is reported in the eCRF but date and value of the corresponding HCV RNA test is missing). This means only patients who had virological response at their last on-treatment or post-treatment measurement, but had no HCV RNA measurements ≥ 70 days post-treatment for reasons not related to safety or effectiveness (e.g. lost-to-follow-up or patient not willing to perform an additional HCV RNA test ≥ 70 days post-treatment) will be excluded from this analysis.

The Safety Population (SP) is defined as all patients who received at least one dose of the ABBVIE REGIMEN.

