## 6 Analysis populations

*The target population (TP)* – all patients, who fulfill the following criteria:

- treatment-naïve or treatment-experienced adult (age at least 18 years) male or female patients with confirmed CHC with genotype 1 (1a and/or 1b) only, receiving combination therapy with the interferon-free ABBVIE REGIMEN  $\pm$  RBV according to standard of care and in line with the current local label. The prescribed ABBVIE REGIMEN needs to be known;
- if RBV is co-administered with the ABBVIE REGIMEN, it has been prescribed in line with the current local label (with special attention to contraception requirements and contraindication during pregnancy);
- patients with voluntarily signed and dated a patient authorization to use and/or disclosure his/her anonymized health data (or informed consent) prior to inclusion into the study;
- patients must not be participating or intending to participate in a concurrent interventional therapeutic study.

Patients who prematurely discontinue earlier than  $\leq$ study day 55 (for 12 weeks treatment) or  $\leq$ study day 139 (for 24 weeks treatment) will be used in analyses on the population with actual EoT time point without windowing conventions adjustment for EoT.

*The core population (CP)* – all patients of the TP, who have started the treatment combination recommended in the current local label for their disease characteristics. Patients, who fulfill at least one of the following conditions, will be excluded from the CP:

- patients with unknown fibrosis status;
- cirrhotic patients with genotype 1a not receiving ribavirin;
- patients with genotype 1 for whom two direct-acting antiviral agents regimen (2DAA) instead of 3DAA is prescribed;
- patients with EoT  $\leq$ study day 55 (for 12 weeks treatment) or  $\leq$ study day 139 (for 24 weeks treatment).

*The safety population (SP)* – all patients who received at least one dose of the ABBVIE REGIMEN.

 This table is based on the table 4 “Analysis time windows” of clinical study Protocol.

 These time windows are intended for the CP allocation filter only. In case of the TP, all patients will be used for the analysis regardless of actual EoT day relevance to EoT time windows.

 This section is based on the sections 9.7.1 “Analysis population, time windows and handling of missing data” and 9.2.1 “Target population” of clinical study Protocol.

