## 8.1 Subject Disposition

Subject disposition will be represented in tables and listings for *all patients who signed the Consent for use/disclosure of data form (informed consent)* and will include the following results:

- the number of subjects who signed the Consent for use/disclosure of data form;
- the number of subjects in each analyzed population;
- the number of subjects who has HCV RNA assessment performed at least 10 weeks post-treatment (i.e.  $\geq 70$  days after EoT);
- the number of subjects without HCV RNA assessment performed at least 10 weeks post-treatment (i.e.  $\geq 70$  days after EoT) and the reasons of it;
- the number of patients with the violations of the eligibility criteria and the corresponding violated inclusion/exclusion criteria.

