## 8.2 Protocol Deviations

The presentation of Protocol deviations is not planned in this study.

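### SAP Table 1.3 counts eligibility violations within the target population, not among all consented patients as SAP 8.1 requires, so on a literal reading its violation rows are zero by construction

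*SAP*

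**What the plan says.** SAP 8.1 (Subject Disposition) states that disposition will be shown in tables and listings for all patients who signed the consent form. Among the required results it names "the number of patients with the violations of the eligibility criteria and the corresponding violated inclusion/exclusion criteria".

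The corresponding shell is "Table 1.3 Violation of eligibility criteria". Its population line is the target population, and its footnote reads "N: the number of subjects in the target population", with percentages taken over that N. The rows run from "Patients with violation of inclusion criteria", through individual inclusion and exclusion criteria, to a closing row for subjects who are fully eligible.

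SAP 6 defines the TP as "all patients, who fulfill the following criteria" and then lists four: genotype 1 chronic hepatitis C treated in line with the local label, label-compliant ribavirin where it is given, signed consent, and no concurrent interventional study. Protocol 9.7.1 agrees: "The target population (TP) is defined as all patients who fulfill the criteria specified in Section 9.2.1". Protocol 9.2.1 is the study's eligibility list and has the same four items.

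Two other places bear on the point. Table 1.1 takes its percentages from consented patients and has a TP row. SAP 8.2 says "The presentation of Protocol deviations is not planned in this study".

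**The concern.** The table is meant to show how many patients failed a criterion, but its population is the group that passed all of them. It also departs from the population that the SAP's own text sets for disposition. A reader of the final report would see full eligibility and could take it as a finding about how patients were selected, when it would be a consequence of the chosen denominator.

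This matters somewhat more in a real-world cohort, where readers want to know how far the analysed patients differ from those enrolled. The plan itself allows for treated patients outside the TP: footnotes to the baseline tables (for example under Table 1.4.1) say what to do if the TP and the safety population turn out to be equal, which implies that they may not be. Table 1.3 is where the reasons for such a difference should appear.

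**Working it through.** No sample size, power or alpha figure is involved, and the shells hold only placeholders. The check is therefore one of set logic.

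**Inputs**
- C: patients who signed consent (the population in SAP 8.1 and the denominator of Table 1.1).
- E: patients who meet every eligibility criterion (Protocol 9.2.1).
- T: the target population, contained in both C and E (SAP 6, Protocol 9.7.1).

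**Table 1.3 as drawn**
- Violation rows: patients in T but not in E. Since T lies inside E, this set is empty, and each row is 0/|T| = 0.0%.
- Closing eligible row: |T and E|/|T| = |T|/|T| = 100.0%.

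**Table 1.3 on the SAP 8.1 population**
- Violation rows: patients in C but not in E, divided by |C|. This can exceed zero.
- Closing row: |C and E|/|C|, which is no longer forced to 100%.

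**Scale.** If the number consented equalled the planned enrolment of 158 (Protocol 9.5; an assumption, since the consented number is not given) and k of them failed a criterion, the corrected table would show k/158. Each such patient counts for 1/158 = 0.6%. The table as drawn shows 0/(158 − k) = 0.0% for any k below 158.

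**What the other planned outputs show**
- Table 1.1 gives |C| and |T|, so |C| − |T| can be read off. It does not say which criterion was failed.
- SAP 8.1 promises listings as well as tables, and SAP 8 says raw data will be listed unless otherwise specified. No listing shell is supplied.
- SAP 8.2 rules out a presentation of protocol deviations, so no summary from that source fills the gap.

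The total outside the TP is therefore available in summary form. The breakdown by criterion is not.

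**The case against.** The strongest objection is that the forced zero is conditional, for two reasons.

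First, the TP may be applied more loosely than it is written. Its opening criterion already requires treatment in line with the local label, yet SAP 6 then forms the core population (CP) by removing TP patients on grounds that include the treatment combination they received. If the TP strictly excluded off-label patients, some of those removals would be redundant. If it does contain such patients, a violation of the first criterion could be counted inside the TP.

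Second, the recorded eligibility items may not match the TP criteria. The SAP was written from Protocol version 4.0 and CRF version 2.0, neither of which is among the documents reviewed. Table 1.3 has exclusion-criterion rows, whereas the available Protocol 9.2.1 has no separate exclusion list. Those rows may be template text or may reflect a different list; the documents do not settle it.

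Both reasons stand as limits on the zero. Neither rescues the table: a looser TP would yield a partial count, with patients outside the TP still omitted against SAP 8.1.

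A reader might also infer that ineligible patients and their reasons would be reported nowhere. The documents do not support that. Table 1.1 gives the total outside the TP, and 8.1 commits to listings that include the violated criteria. SAP 8.2 concerns protocol deviations and does not cancel the separate commitment in 8.1.

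Finally, a programmer following the text of 8.1 would produce the right table. That is fair, but programmers commonly work from the shell, and here header and footnote agree with each other and not with 8.1.

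**Conclusion.** The point holds as an internal inconsistency in reporting. The population and denominator of Table 1.3 contradict SAP 8.1. With the TP definition applied literally and the recorded criteria equal to the TP criteria, the violation rows are 0% and the eligible row 100% by construction. If either assumption fails, a cell could be non-zero, but consented patients outside the TP would still be missing. In both cases no planned summary table gives violations by criterion for the population that 8.1 names.

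The consequence is small. No analysis population definition, confidence interval or SVR12 estimate changes, and nothing here suggests that ineligible patients enter the primary analysis. It might also be tempting to treat the absence of counts by reason for exclusion from the CP as part of the same error. It is not: leaving the CP is not an eligibility violation, and 8.1 does not ask for those counts. This is a minor item, worth correcting because the output would be misleading as drawn.

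**What to change.** Change the population line and the N footnote of Table 1.3 to all patients who signed informed consent, matching SAP 8.1 and Table 1.1. Check at the same time that the inclusion and exclusion rows correspond to the criteria in the protocol version and CRF that the SAP cites, and delete the exclusion rows if there is no such list.

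The cost is an edit to one header and one footnote. No new data are needed, because 8.1 already requires these counts for consented patients.

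Table 1.2 is likewise restricted to the TP although 8.1 lists its contents under disposition. It is not empty by construction, but its population should be reconciled with 8.1 in the same revision. Rows giving the number of patients excluded from the CP for each SAP 6 reason would be a useful optional addition; they are not needed to correct this error and would cost more than the header change.
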